9.4. Treatment Period

At the Week 12 visit of Study APD334-302, subjects will have procedures performed according to the schedule for Study APD334-302. Eligibility for Study APD334-308 will be determined at the Week 12 visit of Study APD334-302 and subjects will be consented/assented. For female subjects, a negative pregnancy test as part of Week 12 APD334-302 procedures is required for entry into Study APD334-308.

After confirmation of eligibility, the 40-Week Treatment Period will begin (Table 7). A study visit window of \pm 7 days is permitted at each visit. Study visits are labeled relative to Day 1 visit date in Study APD334-302 (Figure 1).

The subscores for SF and RB are derived from the subject eDiary entries. On visits when MMS is calculated, these subscores are derived using the scores from the 3 most recent consecutive days within the 7 days prior to the day of bowel preparation (excluding the day of bowel preparation), averaged and rounded to the nearest integer. If 3 consecutive days are not available, then the average of the 2 most recent consecutive days within the 7 days will be used.

On visits without endoscopy, the SF and RB subscores are derived using the scores from the 3 most recent consecutive days within the 7 days prior to the date of visit, averaged and rounded to the nearest integer. If 3 consecutive days are not available, then the average of the 2 most recent consecutive days within the 7 days will be used.

It is recommended that procedures are performed in a consistent order and at approximately the same time of day for each visit. Below is the recommended sequence of events:

- Questionnaire administration
- Adverse event review
- Vital signs
- 12-lead ECG (as indicated in the Schedule of Assessments; Table 7)
- Physical examination
- Extraintestinal manifestations (EIMs; as indicated in the Schedule of Assessments; Table 7)
- PFT (as indicated in the Schedule of Assessments; Table 7)
- OCT (as indicated in the Schedule of Assessments; Table 7)
- Blood sample collection for laboratory tests and predose PK sampling

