10.5.1. Calculation of Modified Mayo Score Component Scores

In general, the MMS symptom scores will be computed from the eDiary data within 7 days prior to the target analysis timepoint (eg, Week 52). Complete details of the MMS symptom score computation method is provided Section 9.4.

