16. APPENDICES

APPENDIX 1: SCHEDULE OF ASSESSMENTS

Table 7: Schedule of Assessments

Visit Label (Based on Continuation from Study APD334-302)	W12/ D85 ^a ± 7 Days	W16/ D113 ± 7 Days	W20/ D141 ± 7 Days	W24/ D169 ± 7 Days	W32/ D225 ± 7 Days	W40/ D281 ± 7 Days	W48/ D337 ± 7 Days	W52/D365 / Early Termination ^b ± 7 Days	2-Week Follow-Up Visit ^c ± 3 Days	4-Week Follow-Up Visit ^c ± 3 Days
Evaluation		1	l	l	l					
Informed consent	X									
Inclusion/exclusion criteria	X									
eDiary review ^d		X	X	X	X	X	X	X		
MMSe								X		
Stool frequency and rectal bleeding subscore ^f		X	X	X	X	X	X	X		
PGA for total Mayo Clinic Score								X		
IBDQ, UC-PRO/SS, SF-36, WPAI-UC, and pain and urgency NRS								X		
Adverse event assessment		X	X	X	X	X	X	X	X	X
Vital signs ^g		X	X	X	X	X	X	X	X	X
12-lead ECG								X		
Physical examination ^h		X	X	X	X	X	X	X	X	X
Extraintestinal manifestations ⁱ								X	X	X
Pulmonary function test ^j					X			X	X	
Ophthalmoscopy with OCTk								X	X	
Pregnancy test ¹		X	X	X	X	X	X	X		X
CBC with differential and platelets		X	X	X	X	X	X	X	X	X
CD4 T-cell count		X	X	X	X	X	X	X	X	X

Visit Label (Based on Continuation from Study APD334-302)	W12/ D85 ^a ± 7 Days	W16/ D113 ± 7 Days	W20/ D141 ± 7 Days	W24/ D169 ± 7 Days	W32/ D225 ± 7 Days	W40/ D281 ± 7 Days	W48/ D337 ± 7 Days	W52/D365 / Early Termination ^b ± 7 Days	2-Week Follow-Up Visit ^c ± 3 Days	4-Week Follow-Up Visit ^c ± 3 Days
Evaluation		·	I	·	·	•	·		l	
Laboratory tests including hs-CRP ^m		X	X	X	X	X	X	X	X	
Stool sample/fecal calprotectin ⁿ				X				X		
Stool sample for microbiome								X		
Flexible proctosigmoidoscopy/ colonoscopy and biopsy °								X		
PK assessments ^p		X	X	X	X	X	X	X	X	X
Biomarkers blood sample ^q								X		
Concomitant medications and procedures ^r		X	X	X	X	X	X	X	X	X
Tuberculosis questionnaires		X	X	X	X	X	X	X	X	X
Tuberculosis tests								X		
Drug dispensation/accountability ^t	X	X	X	X	X	X	X	X		
Study treatment administration ^u	Once daily 12 week Study APD224 202. The Week 12 visit of Study APD224 202 sources as the Day 1 visit of this study.									

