6.3. Retests, Unscheduled Visits and Early Termination Data

For by-visit analyses and summaries, efficacy, safety, HRQoL, and biomarkers data (including scheduled, retests, unscheduled, and early termination) will be assigned to visits after the application of the windowing conventions described in Section 6.4. All measurements will be considered in summaries of abnormalities or worst-case values post Baseline.

Listings will include scheduled, unscheduled, retest, and early termination data.

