6.4. Windowing Conventions

All scheduled study visits are defined relative to Study Day 1 in ADP334-302, the date of first dose in Study APD334-302. Scheduled visit windows are defined in Study APD334-308 Protocol Appendix 1. A windowing convention will be used to determine the analysis visit value for a given measurement and will be applicable for all by-visit summaries and analyses for efficacy and safety data. Refer to Table 2 for specific visit windows.

Table 2 *Visit Windows for Efficacy and Safety Analyses*

For all efficacy (except endoscopy/MMS/histology), efficacy-related biomarkers, safety labs and vital signs.	
Scheduled Study Visit (Protocol Scheduled Day)	Analysis Visit Window (Study Day)
Baseline in Study APD334-302	≤ 1
Week 12 (Day 85 ± 3) in Study APD334-302	72 to 99
Week 16 (Day 113 ± 7)	100 to 127
Week 20 (Day 141 ± 7)	128 to 155
Week 24 (Day 169 ± 7)	156 to 197
Week 32 (Day 225 ± 7)	198 to 253
Week 40 (Day 281 ± 7)	254 to 309

Week 48 (Day 337 ± 7)	310 to 351
Week 52 (Day 365 ± 7)	> 351
For endoscopy/MMS/histology/all composite endpoints that include an endoscopy component and/or RB/SF component, physician's global assessment, health-related quality of life, ECGs, OCT, and PFT.	
Scheduled Study Visit (Protocol Scheduled Day)	Analysis Visit Window (Study Day)
Baseline in Study APD334-302	≤ 1
Week 12 (Day 85 ± 3) ^b in Study APD334-302	66 to 113 (66 to 141 for assessments impacted by COVID-19 pandemic) ^c
Week 32 (Day 225 ± 7) [PFT only]	198 to 253 (198 to 281 for assessments impacted by COVID-19 pandemic) ^c
Week 52 (Day 365 ± 7) ^b	337 to 393 (337 to 421 for assessments impacted by COVID-19 pandemic) ^c

^a Applicable only for subjects who required extended monitoring on Day 2 for vital signs and ECGs.

^b Applicable to all Week 12 and Week 52 efficacy endpoints based on any component of Mayo clinic score, such as clinical remission and symptomatic remission. Protocol visit window for PFT and OCT at Week 12 is Day 85 ± 7 .

^c Assessments impacted by COVID-19 pandemic are reported in the Date of Visit eCRF.

ECG, electrocardiogram; eCRF, electronic case report form; MMS, modified Mayo score; OCT, optical coherence tomography; PFT, pulmonary function test; RB, rectal bleeding; SF, stool frequency

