For cardiac remonitoring upon treatment reinitiation after Day 2, as manifested by more than 1 timed measurement in vital signs or electrocardiogram (ECG) parameters on the same collection date of an unscheduled visit, measurement will be mapped to analysis visit of Cardiac Remonitoring 1, Cardiac Remonitoring 2, etc. in the respective analysis dataset. For analysis, each timed measurement will be programmatically assigned to the nearest hourly timepoint (e.g., Predose, 1-hour Postdose) based on their relationship to the dosing time on the same day. If the dosing date/time on the same day is missing, the timepoint will remain missing. Once mapped, these timed measurements from cardiac remonitoring visits will not be considered for any other analysis visit.

Windowing will be applied prior to any missing data calculations. The last non-missing measurement taken prior to Day 1 (including unscheduled assessments) will be labeled as “Baseline”. Unless stated otherwise, data from all visits including scheduled, unscheduled, and ET visits will be eligible for allocation to an analysis visit. The 2-Week and 4-Week Follow-Up visits will not be included in the visit windows and will be summarized separately without any window applied.

If one or more results for a variable are assigned to the same analysis visit, the result with the date closest to the protocol scheduled day will be used in the analysis, except for component subscores of MMS or TMS, in which case, the composite score and component subscores from the same date will be used in the analysis. If 2 measurements in the same analysis visit window are equidistant from the protocol scheduled study day, the earliest measurement will be used in the analysis. If multiple assessments are available on the same day, then the average of the assessment will be used in the analysis, except for laboratory and ECG data where the

assessment at the earliest time of the same day will be used. If both central and local assessments of the same ECG or lab test are available on the same day, the central result will take precedence over the local result.

For the overlapping visit windows at Week 48 and Week 52, Week 52 will take priority.

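### Giving Week 52 priority in the Week 48/52 overlap leaves Week 48 symptom endpoints only Days 310-336, so an on-schedule Week 48 visit can be counted as non-response

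*SAP*

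**What the plan says.** SAP 6.4, Table 2, has two panels. The first covers efficacy other than endoscopy, modified Mayo score (MMS) and histology. It sets Week 48 at Days 310-351 and Week 52 at any day after 351. The second panel covers endoscopy-based measures and composites with an SF or RB component. It has no Week 48 row, and its Week 52 row reads "337 to 393 (337 to 421 for assessments impacted by COVID-19 pandemic"). Footnote b to that row says: "Applicable to all Week 12 and Week 52 efficacy endpoints based on any component of Mayo clinic score, such as clinical remission and symptomatic remission".

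Symptom endpoints therefore take their Week 48 window from the first panel and their Week 52 window from the second. The SAP settles the resulting overlap in one sentence: "For the overlapping visit windows at Week 48 and Week 52, Week 52 will take priority".

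Three other rules matter:
- **Allocation.** Under SAP 6.3, scheduled, unscheduled, retest and early termination data "will be assigned to visits after the application of the windowing conventions described in Section 6.4".
- **Selection.** When several results share a window, "the result with the date closest to the protocol scheduled day will be used in the analysis". MMS and total Mayo subscores are an exception: they are taken from the same date as the composite.
- **Missing data.** Windowing comes before missing-data handling (SAP 6.4), and SAP 16.2.1 counts missing other-secondary outcomes as non-response.

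The protocol schedules the visit at "W48/ D337 ± 7 Days" (Appendix 1, Table 7), with SF and RB subscores but no MMS. SAP 16.2 lists four symptom endpoints at Week 48: symptomatic remission, complete symptomatic remission, noninvasive clinical response and symptomatic response.

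**The concern.** An analysis window should contain the day on which its visit is scheduled. Here the priority sentence removes the Week 48 target day and every later day from the Week 48 window. A subject who attends exactly on schedule can have a valid symptom score that is used at neither visit and is then imputed as a failure at Week 48.

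The Week 48 response rates of the four endpoints could be lowered, and a dip that reflects only the windowing could appear between Week 40 and Week 52 in the by-visit results. If visit timing is unrelated to arm and outcome, both arms' rates, and the difference between them, shrink by the same factor.

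**Working it through.** **Inputs.** Scheduled days are Week 40 = 281, Week 48 = 337 and Week 52 = 365, each ± 7 (Protocol Table 7). Windows are from SAP Table 2. The planned number is about 35 (Protocol 10.2).

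**1. Reproduce the SAP windows.** The Week 48 limits are midpoints between scheduled days. (281 + 337)/2 = 309, so the window opens on Day 310. (337 + 365)/2 = 351, so it closes on Day 351. That is 42 days. The second-panel Week 52 window is 365 ± 28 = Days 337-393. Both agree with Table 2. The COVID extension changes only the upper limit.

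**2. Where the priority sentence can act.** Within the first panel, 310-351 and > 351 do not overlap, and the second panel has no Week 48 row. The sentence therefore has an effect only where Week 48 comes from the first panel and Week 52 from the second, which means the SF/RB symptom endpoints.

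**3. What Week 48 keeps.** The overlap of 310-351 and 337-393 is Days 337-351, 15 days. The remainder is Days 310-336, or 42 − 15 = 27 days. Permitted Week 48 visit days are 337 ± 7 = 330-344, 15 days. Of these, Days 337-344 fall in the overlap: 8/15 = 53.3%, including the target day.

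**4. What happens to the moved record.** At Week 52 it lies 365 − 337 = 28 to 365 − 344 = 21 days from target. A Week 52 visit on Days 358-372 is at most 7 days away and is chosen. The same-date exception does not rescue the record: Week 48 has no scheduled MMS, so the composite and its subscores come from the Week 52 visit.

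**5. Can Week 48 be refilled?** Permitted Week 40 days are 274-288, outside 310-336. Only an unscheduled or early termination symptom record on Days 310-336 could fill it.

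**6. Size.** The documents give no visit timing and do not say which date a symptom record carries for windowing. All rows assume the ordinary meaning of priority and no other symptom record on Days 310-336.

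| Dating of the record | Assumed Week 48 visit timing | Share lost |
|---|---|---|
| Visit date | all on Days 310-336 | 0% |
| Visit date | even over Days 330-344 | 8/15 = 53% |
| Visit date | all on Day 337 | 100% |
| Last diary day used, k days before the visit | even over Days 330-344 | (8 − k)/15: 47% at k = 1, 20% at k = 5, 13% at k = 6 |
| 7 days before target Day 337 (Days 330-336) | any | 0% |

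The range of k follows from Protocol 9.4. Three consecutive days within the prior seven put the last day used 1 to 5 days before the visit; the two-day fallback extends this to 6.

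If all 35 subjects attended and visits were evenly spread, 35 × 8/15 = 18.7, about 19 records. An assumed true rate of 40% would then be reported as 40% × 7/15 = 18.7%.

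**The case against.** **Priority may mean only order of choice.** The SAP does not define the word. It could mean that Week 52 chooses first and unused records go back to Week 48, in which case a displaced record is not lost. Table 2 also lets Week 12 (66-113) and Week 16 (100-127) overlap without truncating either. This shows that the word is open, but no SAP text provides for a return, and SAP 6.3 allocates by window rather than by nominal visit. Two programmers could legitimately obtain different Week 48 results.

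**Symptom scores may not be dated by visit.** Protocol 10.5.1 speaks of diary data in the 7 days before the target timepoint. For Week 48 that is Days 330-336, wholly inside the retained window, with no loss. This reading stands as a possibility. Against it, the same section continues "Complete details of the MMS symptom score computation method is provided Section 9.4", and Section 9.4 bases scores at visits without endoscopy on diary days "within the 7 days prior to the date of visit, averaged and rounded to the nearest integer". Visit dating is the better-supported reading, but it is not settled.

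**The impact is small.** This is largely right. One of seven timepoints of four other-secondary endpoints is touched, the protocol plans no hypothesis testing, and the SAP's p-values are nominal. Losing a non-responder's record also changes nothing.

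**Stronger readings to avoid.** A reader might infer that at most 19 records are at risk. The documents do not support this as a bound: it is one timing scenario, and visit dating allows up to 100%. A reader might also infer that the Week 52 results are damaged. They are not: the priority sentence takes nothing from Week 52.

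**Conclusion.** The rule is wrong as written. On its ordinary meaning it cuts the Week 48 symptom window from 42 to 27 days, removes the target day, and can turn an on-schedule observation into non-response. The day arithmetic is certain. The harm rests on two conditions that the documents leave open: that overlap records belong to Week 52 without return, and that symptom records carry the visit date or a diary day close to it. The share of Week 48 records lost cannot be fixed from the documents and may be nil.

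The primary and key secondary endpoints are unaffected. The point should be corrected because the sentence has no other function and the remedy is cheap, but it does not threaten the study's main conclusions.

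**What to change.** Replace the priority sentence in SAP 6.4 with a rule to this effect: for SF/RB records on Days 337-351, selection for Week 52 is made first, and any record not selected for Week 52 remains eligible for Week 48. State as well that SF/RB records are windowed by visit date.

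Do not instead hold scheduled Week 48 records at Week 48 by nominal visit. For a subject without a Week 52 visit, a Day 337-351 record can at present supply Week 52 symptomatic remission, a key secondary endpoint. A nominal-visit rule would remove that record and turn the Week 52 outcome into imputed non-response. The proposed rule keeps the record at Week 52; for such a subject Week 48 may still be missing, which is the price of leaving Week 52 results unchanged.

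The cost is one replacement sentence, the short dating statement and a small programming change. No new data are needed.

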6.5. Statistical Tests

Due to the limited number of subjects anticipated to enroll in this study and central randomization not designed to control for allocation ratio in Japan. Point estimate with 95% confidence intervals (CIs) and nominal p-values (2-sided) will be reported.

6.6. Common Calculations

For quantitative measurements:

- Change from Baseline = Test Value at Visit X – Baseline Value
- Percent change from Baseline = $((\text{Test Value at Visit X} - \text{Baseline Value}) / \text{Baseline Value}) \times 100$
- Proportion at Visit X = Number of subjects satisfying criteria at Visit X / Total number of subjects at Visit X

6.7. General Study Information

A general table with summary of study information will be generated, including the date of first subject signed informed consent form (ICF), the last subject visit date, and the database lock date. All analyses will be conducted using SAS® (v9.4 or later, SAS Institute Inc., Cary, NC).

7. DETERMINATION OF SAMPLE SIZE

There is no formal sample size estimation for Study APD334-308. The number of subjects to be enrolled in this study was determined by number of Japanese subjects enrolled in Study APD334-302, and those subjects were eligible to enroll according to Study APD334-308 protocol.

8. STATISTICAL CONSIDERATIONS

8.1. Multicenter Studies

Study APD334-302, the parent study of ADP334-308, was conducted by multiple investigators at multiple centers internationally. Randomization to treatment groups is stratified by:

- Naïve to biologic/JAK inhibitor therapy at APD334-302 study entry (Yes/No)

- Baseline corticosteroid use (Yes/No)
- Baseline disease activity (MMS: 4 to 6 or 7 to 9)

There will be no adjustment for investigational site for this study.

8.2. Adjustments for Covariates and Factors to be Included in Analyses

Due to the limited number of subjects enrolled in this study and central randomization did not control treatment balance in Japanese subjects, unless otherwise specified, only endpoint Baseline measures are used as covariate in the analyses. For details of their inclusion in the models, refer to the specific analysis section.

8.3. Missing data

Missing adverse event (AE) relationship to study drug and AE seriousness will be imputed as described in Section 18.1.1.2 and Section 18.1.3, respectively. Partial or missing AE start dates and concomitant medication start dates will also be imputed as described in APPENDIX 2. No other missing safety data will be imputed.

Missing efficacy data will be handled as described in Section 16.1.2, Section 16.2.2, and Section 16.3.2. In the primary analysis of the primary endpoint and main analyses of all binary responder-type endpoints, all subjects with missing data, regardless of reason for missingness, will be considered as non-responders. In the main analysis of continuous or score endpoints, such as biomarker measures, urgency Numeric Rating Scale (NRS), abdominal pain NRS, and health related quality of life measures, subjects with missing data will be handled using observed cases only.

8.4. Multiple Comparisons/ Multiplicity

There will be no adjustments for multiplicity. Due to the limited number of subjects anticipated to enroll in this study. Point estimate with 95% confidence intervals (CIs) and nominal p-values (2-sided) will be reported.

8.5. Subgroup Analyses

The following subgroups will be assessed for the primary and key secondary endpoints. Baseline is referring to APD334-302:

- Sex (Female/Male)
- Age (\leq or $>$ Median age, and $<$ or \geq 65). This refers to age collected at Screening in Study APD334-302.
- Baseline oral corticosteroid usage (Yes/No)
- Naïve to biologic/JAK inhibitor therapy at APD334-302 study entry (Yes/No)

- Baseline disease activity (MMS: 4 to 6 or 7 to 9)
- Baseline fecal calprotectin (\leq or $>$ median value)
- Baseline total Mayo score (\leq or $>$ 8)
- Duration of UC (\leq or $>$ Median)
- Extent of disease (Proctosigmoiditis/Left-sided colitis, Pancolitis, Proctitis as reported on the eCRF)
 - Proctitis (Yes or No, based on central read)
 - Prior UC treatment of oral 5-aminosalicylic acid (5-ASA) only (Yes or No)
 - Prior UC treatment failure of oral 5-ASA only (Yes or No)
 - Number of prior biologic or JAK inhibitor therapies (1 or $>$ 1)
 - Prior UC treatment failure of anti-tumor necrosis factor alpha (anti-TNF α) (Yes or No)

Additional subgroups may be assessed, if deemed necessary. The medians will be derived based on the FAS for all subgroups cut at the median.

9. OUTPUT PRESENTATIONS

APPENDIX 1APPENDIX 1 contains conventions for presentation of data in outputs.

10. DISPOSITION AND PROTOCOL DEVIATIONS

All subjects who provide informed consent will be accounted for in this study. Inclusion criteria not met and exclusion criteria met will be listed.

Among the enrolled subjects, the number and percent of subjects who completed/ discontinued treatment, reasons off treatment, the number and percent of subjects who completed/discontinued the study, and reasons off study will be summarized. The number and percent of subjects in each analysis set will be summarized for all enrolled subjects. A listing of subjects whose blind was broken during Study APD334-308 will be provided. The number of subjects whose visit was impacted by the COVID-19 pandemic per eCRF will also be summarized by nominal visit.

During site monitoring, protocol deviations will be graded as Critical, Major or Minor.

According to ICH E3 and ICH E3(R1), important protocol deviations are a subset of protocol deviations that might significantly affect the completeness, accuracy, and/or reliability of the study data or that might significantly affect a subject's rights, safety, or well-being (ICH 1995, ICH 2012). For example, important protocol deviations might include enrolling subjects in violation of key eligibility criteria designed to ensure a specific subject population or failing to collect data necessary to interpret primary endpoints, as this may compromise the scientific value of the study.

During the review of all reported deviations, important deviations related to study inclusion or exclusion criteria, conduct of the study, patient management or patient assessment will be identified. Where relevant the importance of a potentially important protocol deviations will be assessed in the context of the study's estimands to evaluate potential impact.

All important protocol deviations will be summarized for the FAS in the following categories in descending frequency in the etrasimod group.

All protocol deviations will be listed, including whether a deviation was impacted by the COVID-19 pandemic (Yes or No). Protocol deviation categories include but are not limited to the following:

- Informed Consent
- Eligibility and Entry Criteria
- Concomitant Medication
- Laboratory Assessment
- Study Procedures
- Serious Adverse Event
- Visit Schedule
- Investigational Product Compliance
- Efficacy
- Administrative
- Source Document
- Regulatory or Ethics Approvals
- Other

Important protocol deviations will also be summarized by whether they were impacted by the COVID-19 pandemic (Yes or No). Additionally, a summary of missing endoscopy regardless of reason and missing endoscopy due to visit impacted by the COVID-19 pandemic will be presented by visit.

